3.6 Exclusion Criteria for Post-surgical Immunotherapy

Patients who are deemed unresectable due to local progression (i.e. without metastatic disease) may continue directly to Cycle 2 immunotherapy without rescreening. No eligibility checklist is necessary for these patients.

Prior Therapy

- 3.6.1 Any anti-neoplastic biologics, vaccines or hormonal treatment, including investigational drugs, within 28 days of the first dose of study combination immunotherapy administration.
- 3.6.2 Patients with a history of past treatment with immunotherapy agents prior to initial enrollment into this study (including, but not limited to: IL-2, interferon, anti-PD-1, anti-PD-L1, anti-PD-L2, anti-CD137, anti-OX-40, anti-CD40, anti-CTLA-4 or anti-CCR2/5 antibodies).
- 3.6.3 Is currently participating or has participated in a study of an investigational agent or using an investigational device for the treatment of cancer. The patient's participation in other clinical trials must be approved by the Principal

A Phase I/II trial of combination immunotherapy with nivolumab and a CCR2/CCR5 dual antagonist (BMS-813160) with or without GVAX following chemotherapy and radiotherapy for locally advanced pancreatic ductal adenocarcinomas (PDACs)

Investigator.

3.6.4 Patients receiving active immunosuppressive agents and chronic use of systemic corticosteroids within 14 days of the first dose of study combination immunotherapy administration.

3.6.5 Patients who have received a live vaccine within 28 days of the first dose of study immunotherapy administration. Examples of live vaccine include, but are not limited to, the following: measles, mumps, rubella, chicken pox, yellow fever, rabies, BCG, and typhoid vaccine.

Note: Seasonal influenza vaccines for injection are generally killed virus vaccines and are allowed. However, intranasal influenza vaccines (e.g. Flu-Mist) are live-attenuated vaccines, and are not allowed within 28 days of study treatment.

3.6.6 Patients receiving growth factors including, but not limited to, granulocyte-colony stimulating factor (G-CSF), GM-CSF, erythropoietin, within 14 days of the first dose of study immunotherapy administration. Use of such agents while on study is also prohibited.

Medical History and Concurrent Diseases

3.6.7 Any evidence of metastatic disease by radiologic imaging

3.6.8 Has a pulse oximetry < 92% on room air.

3.6.9 Requires the use of home oxygen.

3.6.10 Uncontrolled or significant cardiovascular disease including, but not limited to, any of the following:

- Myocardial infarction or stroke/transient ischemic attack within the past 6 months
- Uncontrolled angina within the past 3 months
- Any history of clinically significant arrhythmias (such as ventricular tachycardia, ventricular fibrillation, or torsades de pointes)
- History of other clinically significant heart disease (eg, cardiomyopathy, congestive heart failure with New York Heart Association functional classification III-IV, pericarditis, significant pericardial effusion, or myocarditis)
- Cardiovascular disease-related requirement for daily supplemental oxygen therapy

3.6.11 Evidence of uncontrolled, active infection, requiring parenteral anti-bacterial,

A Phase I/II trial of combination immunotherapy with nivolumab and a CCR2/CCR5 dual antagonist (BMS-813160) with or without GVAX following chemotherapy and radiotherapy for locally advanced pancreatic ductal adenocarcinomas (PDACs)

anti-viral or anti-fungal therapy < 7 days prior to administration of study immunotherapy treatment.

- 3.6.12 Other uncontrolled intercurrent illness including, but not limited to, chronic ongoing infection or psychiatric illness/social situations that would limit compliance with study requirements.
- 3.6.13 Current or recent (within 3 months of study treatment administration) gastrointestinal disease that could impact the absorption of study treatment.
- 3.6.14 Any gastrointestinal surgery that is likely impact upon the absorption of study treatment.
- 3.6.15 Inability to be venipunctured and/or tolerate venous access.
- 3.6.16 Patients who have had surgery within 28 days of the first dose of study combination immunotherapy administration, excluding minor procedures (dental work, skin biopsy, etc.), duodenal stent placement, celiac plexus block, vascular access devices and biliary stent placement. Participants must have recovered from the effects of major surgery or significant traumatic injury at least 14 days before the first dose of study immunotherapy treatment.

Restricted Concomitant Therapy

- 3.6.17 Current or prior use of strong/moderate CYP3A4 inhibitors or inducers within 28 days or 5 half-lives, whichever is shorter, prior to the first dose of BMS-813160. (See **Appendix C**).
- 3.6.18 Current or prior use of Class I antiarrhythmics (eg, quinidine, procainamide, disopyramide, lidocaine, phenytoin, mexiletine, tocainide, flecainide, propafenone, and moricizine) within 28 days of the first dose of BMS-813160.
- 3.6.19 Current use of tricyclic antidepressants

Physical and Laboratory Test Findings

- 3.6.20 Ascites needing paracentesis or medical management.
- 3.6.21 Any of the following on 12-lead electrocardiogram (ECG) prior to study treatment administration, confirmed by repeat.
 - QRS \geq 120 msec, except right bundle branch block
 - QTcF (QT corrected for heart rate using Fridericia's method) \geq 480 msec, except right bundle branch block

A Phase I/II trial of combination immunotherapy with nivolumab and a CCR2/CCR5 dual antagonist (BMS-813160) with or without GVAX following chemotherapy and radiotherapy for locally advanced pancreatic ductal adenocarcinomas (PDACs)

Allergies and Adverse Drug Reaction

- 3.6.22 History of severe hypersensitivity reaction to any monoclonal antibody.
- 3.6.23 History of allergy to study treatments or any of its components of the study arm that participant is enrolling.
- 3.6.24 Patient has a known or suspected hypersensitivity to GM-CSF, hetastarch, corn, dimethyl sulfoxide, fetal bovine serum, trypsin (porcine origin), yeast or any other component of GVAX pancreas vaccine.

Other Exclusion Criteria

- 3.6.25 Women who are pregnant or breastfeeding.
- 3.6.26 Patient is unwilling or unable to follow the study schedule for any reason.

3.7 Inclusion of Women and Minorities

Both men and women of all races and ethnic groups are eligible for this trial.

4. TREATMENT PLAN

4.1 Agent Administration

Treatment will be administered on an outpatient basis. Dosing delays are described in **Section 5.1**. Enrolled patients will receive eight to sixteen 14-day cycles of FOLFIRINOX-based chemotherapy (i.e. FOLFIRINOX, 5-FU/leucovorin, FOLFIRI) and SBRT (6.6. Gy x 5 days). SBRT will be initiated between two to four weeks after completion of chemotherapy. Both chemotherapy and SBRT are considered standard of care. If patients remain eligible for continuation in the study, they will receive one 28-day cycle of combination immunotherapy within two weeks of completion of SBRT.

Due to availability of BMS-813160, study enrollment was closed as of December 19, 2022. Patients randomized prior to this will continue receiving study treatment as planned until drug supply expires on July 31, 2023, then will continue to receive any remaining study cycles without BMS-813160. Patients who were enrolled but not randomized prior to December 19, 2022 (i.e. those receiving chemotherapy) will be assigned to a new arm (Arm C).

In phase I, the combination immunotherapy consists of nivolumab, CCR2/CCR5 dual-antagonist (BMS-813160) and GVAX. In phase II, the first 10 patients (those randomized before December 19, 2022) will be randomized 1:1 between Arm A and Arm B. Remaining patients will be assigned to Arm C. Arm A will receive nivolumab and BMS-813160, and Arm B will receive nivolumab, BMS-813160 and GVAX. Arm C patients will receive nivolumab and BMS-813160 for Cycle 1 (prior to surgery) and then nivolumab and GVAX for Cycles 2 and beyond. Due to the span of time between enrollment and study drug administration (approximately 5-9 months of chemotherapy and SBRT), it is possible we will not know whether to enroll several patients to Phase I or Phase II at the time of their consent. Until a sufficient number of patients have completed their first cycle of study treatment in Phase I to allow us to determine the Phase II dose of BMS-813160, we will inform new study candidates of both possibilities during consent. These patients will sign an informed consent that describes both Phase I and Phase II at the time of enrollment (prior to SOC chemotherapy) and will be informed of their specific phase and sign either a Phase I or Phase II consent form prior to starting study treatment.

Surgery will be scheduled to occur between five to seven weeks after completion of SBRT. Surgery is considered standard of care and only toxicities considered related to study procedures or treatment will be collected from the time of surgery until the start of Cycle 2. If the surgery is scheduled to be after the completion of the 28-day Cycle 1 of combination immunotherapy, anti-CCR2/5 therapy will be continued up to the day before surgery (but a second dose of nivolumab and GVAX will not be administered because this is not considered a new cycle). If the patient is not a surgical candidate, they will undergo an EUS-guided tumor biopsy. Both surgically-resected and non-surgical candidates who are eligible for continuation in the study post-surgical evaluation will continue to receive 4 more 28-day cycles of their assigned combination immunotherapy or till development of metastatic disease.

A Phase I/II trial of combination immunotherapy with nivolumab and a CCR2/CCR5 dual antagonist (BMS-813160) with or without GVAX following chemotherapy and radiotherapy for locally advanced pancreatic ductal adenocarcinomas (PDACs)

For those who undergo a surgery or NanoKnife procedure, immunotherapy will be initiated 6 to 12 weeks after the procedure. For those who are not surgical candidates, the immunotherapy will not be held.

Patients who remain free of metastatic disease at the completion of 5 cycles of combined immunotherapy (1 cycle prior to surgery and 4 cycles post-surgical evaluation) will be eligible to enroll in the optional **Maintenance Treatment Phase**. During the 24-week maintenance phase, Phase I and Arm B patients will receive BMS-813160 daily, nivolumab every four weeks, and GVAX once, Arm A patients will receive BMS-813160 daily and nivolumab every four weeks, and Arm C patients will receive nivolumab every four weeks and GVAX once.

Table 1: Study Regimen

Agent	Pre-medications, Precautions	Dose	Route
GVAX (Cycle 1: Phase 1 and Arm B Cycles 2+: Phase 1, Arm B, and Arm C patients)	EMLA cream (approximately 2.5 g/site at least 1 hour prior to vaccination)	5x10 ⁸ cells	Six intradermal injections every 4 weeks
Nivolumab (All patients)	No prophylactic pre-medications unless indicated by previous experience in an individual subject	480 mg	IV over 30 minutes every 4 weeks*
CCR2/CCR5 dual-antagonist (BMS-813160) (Cycle 1: all patients Cycles 2+: Phase 1, Arm A, and Arm B patients)	No prophylactic pre-medications unless indicated by previous experience in an individual subject	Dose Level 1 (Phase1): 150 mg Dose Level 2 (Phase 1): 300 mg Phase 2 dose: 300 mg	PO twice a day**

*Infusion times are approximate (+25 +/- 10 min) and may need to be adjusted based on subject tolerability.

**At least 8 hours is recommended between doses of BMS-813160.

Please see **Section 5.1** for guidance regarding dosing delays.

4.1.1 GM-CSF Vaccine

The vaccine consists of equal numbers (2.5 x 10⁸ each) of Panc 6.03pcDNA1GM-CSF and Panc 10.05 pcDNA1GM-CSF combined into a single vaccination. Each of the vaccine components consists of a cultured, irradiated, allogeneic pancreatic tumor cell line that has been genetically modified with a plasmid vector encoding the cDNA for human GM-CSF. The final vaccine population secretes approximately 80-100 ng/ 10⁶ cells/ 24 hours of GM-CSF. Vaccine cells from each pancreas tumor cell line frozen at 1.25 x10⁸ cells/vial (2 vials per cell line) in an injectable formulation of Hespan (6%

A Phase I/II trial of combination immunotherapy with nivolumab and a CCR2/CCR5 dual antagonist (BMS-813160) with or without GVAX following chemotherapy and radiotherapy for locally advanced pancreatic ductal adenocarcinomas (PDACs)

Hetastarch in 0.9% sodium chloride with 2% human serum albumin and 5% DMSO) will be thawed on the day of vaccination and taken up into syringes. Each vaccination will consist of six total intradermal injections, two each in the right and left thighs, and two in the non-dominant arm. In the event that the specified limb is contraindicated, the dominant arm may be used. A lidocaine-based topical anesthetic cream will be applied to the injection site at least 1 hour prior to vaccination to diminish the discomfort associated with intradermal injections.

4.1.2 Anti-PD-1 Therapeutic Antibody Nivolumab (Opdivo®, BMS-936558)

Nivolumab is a potent and highly selective humanized monoclonal antibody (mAb) of the IgG4/kappa isotype designed to directly block the interaction between PD-1 and its ligands, PD-L1 and PD-L2. The nivolumab dose that will be used in this study is 480 mg flat dose administered as an intravenous infusion over 30 minutes every 4 weeks. Antiemetic medications should not be routinely administered prior to dosing except as indicated by patient's prior reaction.

4.1.3 CCR2/CCR5 dual-antagonist (BMS-813160)

BMS-813160 is an equipotent and reversible small-molecule dual antagonist of CCR2 and CCR5, and potently inhibits CCR2- and CCR5-dependent functions in response to all known ligands.

Multiple doses of BMS-813160 [10 to 300 mg daily (N=24) and 300 to 900 mg BID (N=18) for 14 days] were safe and generally well tolerated in healthy participants, with no deaths, serious adverse events (SAEs) or discontinuations due to adverse events (AEs).⁴⁰ There was no apparent dose relationship with respect to AEs. All AEs were considered to be mild in intensity, except for one participant who had a headache of moderate intensity while receiving BMS-813160 10 mg QD. There were concentration-dependent increases in QRS and PR intervals and HR at 600 mg BID and 900 mg BID, without any ECG-related AEs or clinical sequelae. The increases in PR (mean < 16 msec at peak), QRS (mean < ~10 msec at peak), and HR (< ~10 bpm at peak) were not considered clinically significant. Concentration-response assessment showed no QTc prolongation.

BMS-813160 was generally safe and well tolerated when administered for 12 weeks to participants with diabetic kidney disease (DKD); 88 participants received BMS-813160 150 mg daily (N = 29), BMS-813160 300 mg BID (N = 30), or placebo (N = 29).⁴² The majority of AEs were mild or moderate in severity. There were no marked differences in AE frequencies in participants receiving BMS-813160 (any dose) compared with placebo, and no dose-related trends were apparent in the frequency of any AEs. The most frequently reported AEs were edema peripheral (6.8% of subjects), fatigue (5.7% of subjects), diarrhea (3.4% of subjects), back pain (3.4% of subjects), and headache (3.4% of subjects).

A Phase I/II trial of combination immunotherapy with nivolumab and a CCR2/CCR5 dual antagonist (BMS-813160) with or without GVAX following chemotherapy and radiotherapy for locally advanced pancreatic ductal adenocarcinomas (PDACs)

BMS-813160 at doses ≥ 300 mg BID results in sustained inhibition of CCR2 and CCR5 on day 14, and was safe and well tolerated in both healthy participants and patients with DKD. The combination of nivolumab, GVAX and BMS-813160 may cause more immune-mediated adverse events than when each therapy is given alone. For this reason, in this study, we will have two dose levels: 150 mg PO BID for dose level 1 and 300 mg PO BID for dose level 2.

BMS-813160 is cleared by metabolism, direct urinary and biliary/fecal excretion. The metabolism of BMS-813160 is primarily mediated via cytochrome P450 3A4, with some contribution from CYP3A5, and is also a substrate for P-glycoprotein (P-gp). Hence, there is potential for drug-drug interactions if BMS-813160 is co-administered with inhibitors or inducers of CYP3A or P-gp. BMS-813160 is not expected to alter the clearance of compounds that are CYP, UGT, or P-gp substrates. However, BMS-813160 and its prominent metabolite, BMS-939429, inhibited MATE1. See **Section 4.3** for restrictions on co-medications.

4.2 General Concomitant Medication and Supportive Care Guidelines

4.2.1 GVAX Pancreas Vaccine

Local skin reactions at vaccine sites may be treated with cold packs, topical lotions (e.g. aloe vera or vitamin E). Pruritus can be managed with topical or systemic benadryl. Significant local inflammation leading to severe pain may be treated with oral analgesics. Local ulceration should be managed with local wound care, with or without antibiotics, and should be evaluated on a case-by-case basis.

4.2.2 Nivolumab

Nivolumab is a fully humanized monoclonal antibody. Subjects should be closely monitored for potential adverse reactions during antibody infusion and potential adverse events throughout the study.

Unexpected Grade 3 or greater laboratory abnormalities should be repeated within 24-72 hours if clinically indicated and monitored as necessary to determine if event meets toxicity criteria.

4.2.2.1 Infusion Reactions

Infusion reactions, including high-grade hypersensitivity reactions, following administration of nivolumab are uncommon. 6.4% (127/1994) and 2.5% (10/407) had infusion reactions when nivolumab was given as a single agent and in combination with ipilimumab, respectively. Severe infusion reactions have been reported in less than 1.0% of patients in clinical trials. Infusion reactions may

consist of fever, chills, shakes, itching, rash, hypertension or hypotension, or difficulty in breathing during and immediately after administration of nivolumab.

Discontinue nivolumab for severe and life-threatening infusion reactions. Interrupt or slow the rate of infusion in patients with mild or moderate infusion reactions.

Patients should be closely monitored for such reactions. Guidelines for patients who experience an infusion related or allergic reaction during or after infusion with nivolumab are shown below.

Table 2: Guidance on Infusion and Hypersensitivity Reactions

NCI CTCAE Grade	Treatment	Premedication at subsequent dosing
Grade 1 Mild reaction; infusion interruption not indicated; intervention not indicated	Increase monitoring of vital signs as medically indicated until the subject is deemed medically stable in the opinion of the investigator.	None
Grade 2 Requires infusion interruption but responds promptly to symptomatic treatment (e.g., antihistamines, NSAIDS, narcotics, IV fluids); prophylactic medications indicated for <=24 hours	Stop Infusion and monitor symptoms. Additional appropriate medical therapy may include but is not limited to: IV fluids, Antihistamines, NSAIDS, Acetaminophen, Narcotics Increase monitoring of vital signs as medically indicated until the subject is deemed medically stable in the opinion of the investigator. If symptoms resolve within one hour of stopping drug infusion, the infusion may be restarted at 50% of the original infusion rate (e.g., from 100 mL/hr to 50 mL/hr). Otherwise dosing will be held until symptoms resolve and the subject should be pre-medicated for the next scheduled dose.	Subject may be pre-medicated 1.5h (\pm 30 minutes) prior to infusion of nivolumab with: Diphenhydramine 50 mg PO (or equivalent dose of antihistamine). Acetaminophen 500-1000 mg PO (or equivalent dose of antipyretic).
Grade 3 Prolonged (i.e., not rapidly responsive to symptomatic medication and/or brief interruption of infusion); recurrence of symptoms following initial improvement; hospitalization indicated for other clinical sequelae (e.g., renal impairment, pulmonary infiltrates)	Stop Infusion and monitor symptoms. Additional appropriate medical therapy may include but is not limited to: IV fluids, Antihistamines, NSAIDS, Acetaminophen, Narcotics, Oxygen, Vasopressors, Corticosteroids, Epinephrine Increase monitoring of vital signs as medically indicated until the subject is deemed medically stable in the opinion of the investigator. Hospitalization may be indicated. Subject is permanently discontinued from further trial treatment administration if the Grade 3 infusion reaction does not return to Grade 1 in less than 6 hours or if the subject requires vasopressors or epinephrine.	Subject may be pre-medicated 1.5h (\pm 30 minutes) prior to infusion of nivolumab with: Diphenhydramine 50 mg PO (or equivalent dose of antihistamine). Acetaminophen 500-1000 mg PO (or equivalent dose of antipyretic).

A Phase I/II trial of combination immunotherapy with nivolumab and a CCR2/CCR5 dual antagonist (BMS-813160) with or without GVAX following chemotherapy and radiotherapy for locally advanced pancreatic ductal adenocarcinomas (PDACs)

NCI CTCAE Grade	Treatment	Premedication at subsequent dosing
Grade 4: Life-threatening; pressor or ventilatory support indicated	
Stop Infusion and monitor symptoms.
 
Additional appropriate medical therapy may include but is not limited to:
 
IV fluids, Antihistamines, NSAIDS, Acetaminophen, Narcotics, Oxygen, Pressors, Corticosteroids, Epinephrine
 
Increase monitoring of vital signs as medically indicated until the subject is deemed medically stable in the opinion of the investigator.
 
Hospitalization is indicated.
 
Subject is permanently discontinued from further trial treatment administration.
	No subsequent dosing
Appropriate resuscitation equipment should be available in the room and a physician readily available during the period of drug administration.		

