3) Nonhepatic Nonhematologic DLT

- a) Grade 2 or greater episcleritis, uveitis, or iritis
- b) Any other Grade 2 eye pain or blurred vision that does not respond to topical therapy and does not improve to Grade 1 severity within 2 weeks OR requires systemic treatment
- c) Grade 2 myocarditis
- d) Grade 3 pneumonitis, bronchospasm, or neurologic toxicity requires discontinuation
- e) Any Grade 3 or greater nondermatologic, nonhepatic, nonhematologic toxicity will be considered a DLT with the following specific EXCEPTIONS:
 - i. Grade 3 electrolyte or laboratory abnormalities that are not complicated by associated clinical adverse experiences, last less than 48 hours and either resolve spontaneously or respond to conventional medical intervention
 - ii. Grade 3 or 4 elevation of amylase or lipase not associated with clinical or radiographic evidence of pancreatitis
 - iii. Grade 3 nausea, vomiting, or diarrhea that lasts less than 48 hours and either resolves spontaneously or responds to conventional medical intervention
 - iv. Isolated Grade 3 fever not associated with hemodynamic compromise (e.g. hypotension, clinical or laboratory evidence of impaired end-organ perfusion)
 - v. Grade 3 endocrinopathy that is well-controlled by hormone replacement
 - vi. Grade 3 tumor flare (defined as pain, irritation, or rash that localizes to site of known or suspected tumor)

A Phase I/II trial of combination immunotherapy with nivolumab and a CCR2/CCR5 dual antagonist (BMS-813160) with or without GVAX following chemotherapy and radiotherapy for locally advanced pancreatic ductal adenocarcinomas (PDACs)

- vii. Grade 3 fatigue
- viii. Grade 3 infusion reaction that returns to Grade 1 in less than 6 hours as long as vasopressors or epinephrine were not required

4) Dermatologic DLT

- a) Grade 3 rash if no improvement (ie, resolution to \leq Grade 1) after a 1- to 2-week dosing delay
- b) Grade 4 rash of any duration

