4.9 Criteria for Removal from Study Treatment

Patients will be removed from study treatment when any of the criteria listed below applies. The reason for study treatment removal and the date the patient was removed must be documented in the Case Report Form.

A subject must be discontinued from the trial for any of the following reasons:

- The subject or legal representative (such as a parent or legal guardian) withdraws consent, or
- Patient is lost to follow-up.

A subject must be discontinued from treatment (but may continue to be monitored in the post-treatment follow-up portion of the trial) for any of the following reasons:

- The subject or legal representative (such as a parent or legal guardian) withdraws consent for treatment,
- Development of distant metastatic disease,
- Intercurrent illness that prevents further administration of treatment,
- Dose-limiting toxicities with exceptions to treatment discontinuation as described in **Section 4.6**,
- Fulfilling criteria for permanent discontinuation of BMS-813160 (see **Section 5.2.6.2**),

A Phase I/II trial of combination immunotherapy with nivolumab and a CCR2/CCR5 dual antagonist (BMS-813160) with or without GVAX following chemotherapy and radiotherapy for locally advanced pancreatic ductal adenocarcinomas (PDACs)

- Unacceptable toxicity/toxicities with exceptions to treatment discontinuation as described in **Section 4.7**,
- Need for >2 dose delays due to the same toxicity as per the dose delay guidelines (see **Section 5.1**),
- If any one or more of the study drugs (nivolumab, BMS-813160 and/or GVAX) are discontinued,
- Inability to reduce corticosteroid dose for immune-related adverse reactions to ≤ 10 mg prednisone or equivalent per day,
- Any dosing delay lasting > 28 days will be cause for permanent discontinuation. Extensions to the period of dose delays may be granted for individual participants on a case-by-case basis after specific consultation and agreement between Principal Investigator, IND Sponsor and BMS in settings where benefit/risk may justify continued study treatment (e.g. participant deriving clinical benefit who requires prolonged steroid taper for management of non-DLT immune-related AEs or experiences delays for management of a non-drug-related AE).

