- Grade 3: Severe or medically significant but not immediately life-threatening; hospitalization or prolongation of hospitalization indicated; disabling; limiting self-care activities of daily living
- Grade 4: Life-threatening consequences; urgent intervention indicated
- Grade 5: Death related to AE

Any AE that changes in grade during its course will be recorded in the CRF at the highest level experience by the subject.

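### Section 4.2.2.1 gives two opposite rules for a Grade 3 infusion reaction that is back to Grade 1 in under 6 hours without vasopressors or epinephrine

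*Combined protocol and SAP*

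**What the plan says.** The paragraph in Section 4.2.2.1 gives two handling rules. The first is "Discontinue nivolumab for severe and life-threatening infusion reactions". The second is "Interrupt or slow the rate of infusion in patients with mild or moderate infusion reactions". Neither carries a time limit, a recovery condition or an exception. The next paragraph points to guidance below it, which is Table 2.

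Table 2 sorts the action by grade:

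- **Grade 1** is described as mild, with no need to interrupt the infusion. The only action is closer monitoring of vital signs.
- **Grade 3**: the infusion is stopped, and the patient is permanently discontinued "if the Grade 3 infusion reaction does not return to Grade 1 in less than 6 hours or if the subject requires vasopressors or epinephrine". The column on later dosing reads "Subject may be pre-medicated 1.5h", followed by the agents.
- **Grade 4**: permanent discontinuation with no condition attached. The column on later dosing reads "No subsequent dosing".

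Four other sections bear on the point:

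- Section 6.2 defines the grade: "Grade 3: Severe or medically significant but not immediately life-threatening".
- Section 4.6 excepts from dose-limiting toxicity a "Grade 3 infusion reaction that returns to Grade 1 in less than 6 hours as long as vasopressors or epinephrine were not required", and Section 4.7 makes the same exception for unacceptable toxicity.
- Section 4.9 lists among the reasons for stopping treatment: "If any one or more of the study drugs (nivolumab, BMS-813160 and/or GVAX) are discontinued".
- Section 1.7 takes patients off the trial when an adverse event leads to discontinuation of any of the three agents.

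**The concern.** Staff managing an acute reaction have two instructions in one subsection, and for some reactions they lead to opposite actions. On one reading, a patient whose Grade 3 reaction settles quickly loses every study drug. On the other, the patient may receive nivolumab again. The choice is a patient-safety matter, and it also decides whether that patient goes on with study treatment.

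There is an accounting side as well. Under the sentence, a patient could be taken off all treatment for an event that Sections 4.6 and 4.7 count neither as a dose-limiting nor as an unacceptable toxicity.

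**Working it through.** The plan gives no figure of its own to reproduce here. The check is a comparison of text, followed by a bound on frequency.

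**1. Does *severe* mean Grade 3?** The paragraph uses mild, moderate, severe and life-threatening. These are the labels that Section 6.2 gives to Grades 1 to 4. Table 2 itself calls Grade 1 mild and Grade 4 life-threatening. Reading severe as Grade 3 follows.

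**2. Does *discontinue* mean ending the drug?** The paragraph sets it against interrupting or slowing the infusion. The same verb covers life-threatening reactions, which Table 2 ends permanently. So it means more than stopping that day's infusion.

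**3. The two rules side by side.**

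| Reaction | Paragraph | Table 2 | Same? |
|---|---|---|---|
| Grade 1 | Interrupt or slow the infusion | Monitor only | No |
| Grade 2 | Interrupt or slow the infusion | Stop; restart at half rate if symptoms clear within an hour | Yes, in substance |
| Grade 3, at Grade 1 in under 6 hours, no vasopressors or epinephrine | Discontinue nivolumab | Not permanently discontinued; later dose foreseen, premedication optional | No |
| Grade 3, slower or needing either agent | Discontinue nivolumab | Permanently discontinued | Yes |
| Grade 4 | Discontinue nivolumab | Permanently discontinued | Yes |

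**4. Following the third row through the protocol.** Under the paragraph, nivolumab is discontinued. Section 4.9 then ends study treatment because one drug has stopped, and Section 1.7 takes the patient off the trial. Under Table 2, nivolumab is not discontinued, so neither provision is triggered, and the exceptions in Sections 4.6 and 4.7 apply.

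**5. How often.** Inputs:

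- Severe infusion reactions in under 1.0% of patients (Section 4.2.2.1).
- At most 12 patients in Phase I and 15 in Phase II (Section 12.2), so 12 + 15 = 27.

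Expected severe reactions: fewer than 0.01 × 27 = 0.27. This counts all severe reactions, so it is an upper bound for the subset in conflict.

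For the Grade 1 mismatch, only a ceiling is available. Section 4.2.2.1 gives any-grade rates of 10/407 = 2.5% (with ipilimumab) and 127/1994 = 6.4% (single agent). These give 0.025 × 27 = 0.7 and 0.064 × 27 = 1.7 patients with a reaction of any grade. The documents do not say what share is Grade 1.

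**The case against.** The strongest reply is that the table governs and the sentence is only a summary of it. The paragraph hands over to Table 2 for guidance. Sections 4.6 and 4.7 repeat the table's condition. Section 4.9, where it removes patients for dose-limiting or unacceptable toxicity, carries over the exceptions in those two sections. This is a fair account of where most of the text points. But nothing says that the table overrides the sentence. Section 4.9 also has its separate ground, that any one drug has been discontinued, and that ground has no exception.

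A second reply is that *discontinue* here means only stopping the infusion, since elsewhere the protocol often adds *permanent* when it means the end of treatment. That is possible, but it fits poorly with the contrast and the shared verb noted in step 2.

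A third is that Table 2 describes Grade 3 as prolonged and never uses the word severe. That is true. The link comes from Section 6.2, and it is the natural one because the paragraph's four words match that scale.

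The reply on impact stands. The event is rare, and enrollment closed on December 19, 2022, which limits future exposure. The Grade 1 mismatch has no bearing on discontinuation.

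**Conclusion.** Section 4.2.2.1 contradicts itself for Grade 3 reactions that return to Grade 1 in less than 6 hours without vasopressors or epinephrine and, with less consequence, for Grade 1 reactions. It is an internal contradiction in a safety rule, not a design choice. Fewer than 0.27 severe reactions are expected in the whole trial. That figure assumes the quoted nivolumab rate carries over to this combination and that both phases reach their maximum size.

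A reader might infer three stronger things, which the documents do not support:

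- **That every severe reaction is in dispute.** The rules agree for Grade 4, and for Grade 3 reactions that are slower to settle or need vasopressors or epinephrine.
- **That Table 2 orders re-dosing.** It makes discontinuation conditional and provides optional premedication, so it permits a further dose by implication only.
- **That the primary analysis is materially at risk.** Section 12.4 does limit the evaluable set to patients who completed one cycle, so one removal in Cycle 1 would cost 1/10 = 10% to 1/8 = 12.5% of a group of 8 to 10. But fewer than 0.01 × 10 = 0.10 severe reactions are expected in a group of 10, and no effect on the analysis is shown.

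No position is taken on which clinical rule is right.

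**What to change.** The sponsor must reconcile the paragraph in Section 4.2.2.1 with Table 2, for Grade 3 and for Grade 1 reactions, so that one rule stands for each, and must state which text governs. Sections 4.6 and 4.7 already match Table 2. They need changing only if the reconciled rule departs from it, and Section 4.9 should then be checked for consistency.

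The cost is a sentence or two of protocol wording, or slightly more if Sections 4.6 and 4.7 have to follow. Sample size and the statistical analyses are not affected.
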